5.4.3.3 Sensitivity analysis for Primary Objective (on Primary PK endpoints)

The analysis described in Section 5.4.3.2 will be repeated on the normalized PK parameters using the same ANOVA model.

For the C_{max} normalization:

$$C_{max_w} = C_{max} / BW, \text{ body-weight normalization}$$

$$C_{max_d} = C_{max} / Dose, \text{ dose normalization}$$

$$C_{max_wd} = C_{max} / (BW * Dose), \text{ body-weight and dose normalization}$$

(BW=Day -1 bodyweight)

For the AUC_{inf} and AUC_{0-t} similar normalization will be used.

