### **Treatment groups and duration**

Part A consists of the following (for a total duration of up to 68 days):

- A 28-day Screening Period (2 to 28 days before administration of study medication)
- A Baseline health status on admission to study site on Day -1.
- 6 treatment periods (each treatment period is followed by a 4-day Washout Period)
  - The first 3 periods include the evaluation of UCB0599 PK following its single-dose administration (180mg) of each formulation under normal gastric pH conditions.
  - The second 3 periods include the evaluation of UCB0599 PK following its single-dose administration (180mg) of each formulation under the condition of elevated gastric pH. The elevated gastric pH will be achieved by co-administering esomeprazole 40mg once daily (QD) over the duration of the 3 treatment periods (Day 14 to Day 33; [Table 1-1](#)).
- A 7-day Safety Follow-Up (SFU) Period

In Treatment Period 1 through Period 3 for Part A, study participants will fast overnight for at least 10 hours prior to study medication administration on Day 1, Day 6, and Day 11, according to the randomization scheme (see [Table 1-1](#)), and will continue to fast for at least 4 hours post-study medication administration; thereafter participants will be given a standard breakfast or light snack. In Treatment Period 4 through Period 6, study participants will fast overnight for at least 9 hours prior to esomeprazole administration on Day 19, Day 24, and Day 29, and will continue to fast prior to study medication administration (1 hour following esomeprazole administration) and for at least 4 hours post-study medication administration (see [Table 1-1](#)); thereafter, participants will be given a standard meal (ie, lunch). In between each Treatment Period, participants will undergo a 4-day Washout Period. On other days during the Treatment Period, study participants will receive standard meals and snacks at appropriate times as indicated by the clinic center (see [Table 1-3](#)). During the whole treatment, participants will remain under close medical supervision in the clinic.

On Day 33, after all the scheduled procedures have been performed, the participant may leave the clinic provided that, in the opinion of the Investigator, there are no safety concerns. Study

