#### **9.4.2.2 Part B**

The primary objective of Part B is to evaluate the plasma PK of UCB0599 after administration of a single dose of an oral formulation in healthy participants of Japanese and Chinese origins.

The PK parameters ( $C_{max}$ ,  $AUC_{0-t}$ , and  $AUC_{inf}$ ) will be used to estimate the following:

- PK parameters for the 3 groups (Part A healthy participants, Japanese participants, and Chinese participants)
- Dose proportionality for each group, including graphical presentation

Individual concentration-time profiles will be displayed graphically on a linear-linear scale and semilogarithmic scale.

Overall geometric mean plasma concentration-time curves and corresponding 95% CIs will be displayed by group.

No formal comparison will be made.

The PK analyses will be performed on the PK data from Part B.

The plasma concentration-time profiles and PK parameters of UCB0599 will be summarized by dose level and group using descriptive statistics (number of available observations, arithmetic mean, standard deviation, geometric mean, coefficient of variation of geometric mean, median, minimum, and maximum). Values below the LLOQ will be reported with a clear sign indicating that they were below the LLOQ. Descriptive statistics of concentrations will be calculated if at least two-thirds of the individual data points are quantifiable ( $\geq LLOQ$ ).

Descriptive statistics will be executed for all PK parameters estimated by ethnicity and dose. For  $t_{max}$ , only the median, minimum, and maximum will be reported.

The PK descriptive statistics from Part A healthy participants who receive 180mg dose of the formulation used in Part B will be presented alongside.

Dose proportionality for  $C_{max}$ ,  $AUC_{0-t}$ , and  $AUC_{inf}$  will be examined for each ethnic group and for Part A healthy participants who receive a 180mg dose of the formulation used in Part B and graphically reported. Dose proportionality could be achieved by dose normalization and log-transforming  $C_{max}$  and AUC data, in which a linear regression  $C_{max}$  versus dose and AUC versus dose will be used to assess if the slope of the regression line deviates statistically significantly from zero. If the slope is not different from zero, then it can be concluded that the PK is proportional to dose.

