The co-primary PK endpoint data obtained for the UCB0599 formulation used in Part B at the 180mg dose under normal gastric pH condition for the three ethnicities (ie, N=36 participants from Part A, N=8 participants of Japanese origin, and N=8 participants of Chinese origin) will be log-transformed. As an exploratory analysis, transformed data will be combined into an Analysis

of Variance (ANOVA) model with fixed effect terms for cohort, assuming the data for each ethnicity come from a single parallel arm design. Point estimates for the geometric mean ratios and corresponding 90% CIs will be obtained and compared between the Japanese participants versus the Part A participants, and between the Chinese participants versus the Part A participants using least squares means and root mean squares of error from the model with subsequent exponential transformation.

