5.4.3.2 Exploratory analysis for Primary Objective (on Primary PK endpoints)

The co-primary PK endpoint data obtained for the groups will be log-transformed. For each dose level, the transformed data will be combined into an ANOVA model with fixed effect terms for participant group. The model may be adjusted for age, height and weight. Therefore, the impact of the Baseline (Day-1) characteristics of age, height and weight will be included in the statistical

model as fixed effect and tested by 10% significant level individually. If a fixed term has a significant effect to the model for all three primary PK parameters at 10% significant level, the term will be included to the ANOVA model as fixed effect. The SAS PROC MIXED procedure will be used. Point estimates for the geometric mean ratios and corresponding 90% CIs will be obtained and compared between the Japanese participants versus the Part A participants (healthy participants on normal gastric condition on the formulation chosen for Part B), and between the Chinese participants versus the Part A using least squares means and root mean squares of error from the model with subsequent exponential transformation.

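### Part B body-weight normalisation runs the wrong way: at fixed mg doses the SAP divides exposure by weight instead of multiplying (minor; descriptive and exploratory results only)

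*SAP*

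**What the plan says.** SAP 5.4.3.3 gives three normalised versions of Cmax: divided by body weight, divided by dose, and divided by both, the last written as "C_{max_wd} = C_{max} / (BW * Dose". AUC0-t and AUCinf are to be treated alike. Weight is specified as "BW=Day -1 bodyweight".

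These values have two uses.

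- **Group comparison.** SAP 5.4.3.3 states: "The analysis described in Section 5.4.3.2 will be repeated on the normalized PK parameters using the same ANOVA model". Under SAP 5.4.3.2, "For each dose level, the transformed data will be combined into an ANOVA model with fixed effect terms for participant group", giving ratios of Japanese and Chinese participants to Part A. It adds: "The model may be adjusted for age, height and weight". A covariate is kept only if it is significant at 10% for all three PK parameters.
- **Descriptive endpoints.** Cmax/BW/D and the two AUC/BW/D quantities are listed as other PK endpoints in Protocol Table 3-2 and 9.4.3.2, and in SAP Table 1-2, 5.4.1 and 5.4.3.4.

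Part B doses are 90, 180 and 360 mg regardless of weight. Part A used one dose level only: "single-dose administration (180mg) of each formulation under normal gastric pH conditions". Protocol 9.4.2.2 limits the exploratory comparison to data "at the 180mg dose under normal gastric pH condition for the three ethnicities" and says of the Part B PK analysis: "No formal comparison will be made". Neither document gives a reason for dividing exposure by weight.

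**The concern.** A weight normalisation should remove the part of a group difference that comes only from body size. At a fixed mg dose a lighter person receives more mg per kg, so exposure is usually flat or higher at lower weight. Dividing by weight then raises the lighter person's value again. In an ethnobridging study, a lighter group would look more different from Part A after normalisation than before it, the reverse of what the label promises. The descriptive BW/D summaries would also carry extra spread from weight.

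Three smaller gaps affect the same analysis:

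- The SAP asks for the comparison at each dose level but defines no Part A comparator at 90 or 360 mg.
- It does not say whether using the same ANOVA model means selecting covariates again on the normalised data or carrying over the selection made on the raw data.
- It cites Day -1 weight, whereas the schedules (Protocol Tables 1-3 and 1-4) and Protocol 8.2.1 place weight at Screening only.

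**Working it through.** The plan states no numerical result here, so there is none to reproduce. The check is algebra plus illustration.

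**Inputs from the documents.** Fixed mg doses; 36 Part A, 8 Japanese and 8 Chinese participants at 180 mg (Protocol 9.4.2.2); eligible weight 45–100 kg for women and 50–100 kg for men (Protocol 5.1); the 10% selection rule (SAP 5.4.3.2).

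**Assumed.** Mean weights 75 vs 60 kg, 76 vs 68 kg and 70 vs 70 kg (Part A vs Part B group); exposure proportional to Dose×BW^-b with b from 0 to 1; log-weight SD 0.15; between-participant log SD 0.35; correlation among the three parameters 0.6 and 0.9; no true ethnic difference.

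**Step 1: direction.** Normalising to the mg/kg dose is C/(Dose/BW) = C×BW/Dose. Using the standard relation CL/F = Dose/AUCinf, which the SAP does not write out, AUCinf×BW/Dose is the reciprocal of clearance per kg. The dependence on weight is then:

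- raw: BW^-b
- SAP form: BW^-(1+b)
- C×BW: BW^(1-b)

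For 50 vs 100 kg at b = 1 the ratios are 2^1 = 2.0 raw, 2^2 = 4.0 SAP and 2^0 = 1.0 for C×BW.

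**Step 2: group ratio without a weight covariate.** With r = Part A weight / Part B weight, the ratios are r^b, r^(1+b) and r^(b-1).

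| Weights | b | Raw | SAP | C×BW |
|---|---|---|---|---|
| 75 vs 60 kg (r = 1.25) | 0 | 1.00 | 1.25 | 0.80 |
| | 0.5 | 1.12 | 1.40 | 0.89 |
| | 1 | 1.25 | 1.56 | 1.00 |
| 76 vs 68 kg (r = 1.118) | 0 | 1.00 | 1.12 | 0.89 |
| | 0.5 | 1.06 | 1.18 | 0.95 |
| | 1 | 1.12 | 1.25 | 1.00 |

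At 180 mg, Dose is the same in every group and cancels. The dose-normalised ratio repeats the raw one, and weight is the only active term in this sensitivity analysis.

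**Step 3: group ratio with the SAP's covariate selection.** Simulation at 180 mg, 4,000 trials per setting, linear weight term, kept if p < 0.10 for all three parameters; 75 vs 60 kg:

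| b | Weight kept, raw data | Weight kept, C/BW data | SAP ratio, re-selected | SAP ratio, raw selection carried over | Unnormalised ratio, raw selection |
|---|---|---|---|---|---|
| 0 | 1–5% | 79–84% | 1.03–1.04 | 1.24–1.25 | – |
| 0.5 | 22–33% | 98.4–98.9% | 1.02–1.03 | 1.23–1.28 | 1.06–1.07 |
| 0.75 | 50–60% | 99.8% | 1.02–1.03 | 1.16–1.21 | 1.05–1.07 |
| 1 | 77–84% | 100% | 1.02–1.03 | 1.08–1.12 | 1.03–1.05 |

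For 76 vs 68 kg and b ≥ 0.5, the re-selected ratio is 1.01. The carried-over ratios are 1.11–1.14 (b = 0.5), 1.07–1.09 (b = 0.75) and 1.04 (b = 1). With equal weights every ratio is 0.99–1.01.

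With ln(weight) in the model, raw and C/BW data give identical group ratios, because ln(C/BW) = ln C − ln BW only lowers the ln(weight) coefficient by 1. The simulated value was 0.99–1.01 in all settings.

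**Step 4: descriptive spread within one group.** Geometric CV = sqrt(exp(v) − 1), with v = 0.35² + (k×0.15)² and |k| = b (raw), 1+b (SAP) or 1−b (C×BW). At b = 1 under the SAP form, v = 0.1225 + 0.0900 = 0.2125, so CV = 48.7%.

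| b | Raw | SAP | C×BW |
|---|---|---|---|
| 0 | 36.1% | 39.5% | 39.5% |
| 0.5 | 37.0% | 43.5% | 37.0% |
| 1 | 39.5% | 48.7% | 36.1% |

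**Step 5: comparator dose.** If Part A 180 mg data served as comparator at 90 or 360 mg, unnormalised ratios under dose proportionality would be 90/180 = 0.5 or 360/180 = 2. Dose normalisation would remove this effect.

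**The case against.** The strongest reply has four parts.

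- **The sizes are assumed.** Both parts share the same weight and BMI limits, and nothing says Part B participants will be lighter. This stands: the direction follows for any b ≥ 0, but the size cannot be fixed from the documents.
- **The SAP may already protect the group ratio.** Covariate selection is part of the analysis to be repeated. If weight is re-selected on the normalised data, almost nothing is left of the distortion. This also stands, but the wording allows the other reading, and the descriptive summaries have no such protection.
- **C×BW is not neutral.** It over-corrects when b < 1 and lies further from 1 than the raw ratio when b < 0.5. At b = 0 it is as far off on the log scale as the SAP form (0.80 against 1.25). That limits the remedy without rescuing the SAP formula: for every b > 0, C×BW is closer to 1 than C/BW, and exact removal by C/BW would need exposure to rise in proportion to weight (b = −1).
- **Nothing important depends on it.** Unnormalised Cmax and AUC, and CL/F, are reported alongside, and the comparison is exploratory. This is right and sets the severity.

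The dose-level, covariate and weight-date gaps are separate from the direction error. The CRF is not available here, so Day -1 weighing cannot be ruled out.

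**Conclusion.** The concern holds, as a minor error in a supporting analysis. As written, the formula strengthens the weight effect whenever exposure is flat or falls with weight, and the plan offers no reason to expect the opposite.

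The distortion of the group ratios depends on three unknowns: the difference in group weights, b, and whether weight enters the model. It ranges from none (equal weights) or about 1.02–1.03 (75 vs 60 kg, weight re-selected, b ≥ 0.5) to 1.56 against a raw 1.25 (75 vs 60 kg, b = 1, no weight covariate). The widening of the BW/D summaries does not need a weight difference between groups. The co-primary PK endpoints, the dose-proportionality power model and the safety analyses are unaffected.

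**What to change.** Two changes matter:

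1. Report the Japanese and Chinese versus Part A ratios with and without a pre-specified ln(body weight) covariate. This does not assume b = 1, and it settles the group comparison whichever normalisation is used.
2. Replace C/BW and C/(BW×Dose) by C×BW and C×BW/Dose for Cmax, AUC0-t and AUCinf. State that this assumes exposure inversely proportional to weight, and give the limits of that assumption. Align the BW/D endpoint labels in the SAP and, at the next amendment, in the protocol.

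Three clarifications can go into the same update:

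3. Limit the ratio to Part A to 180 mg, as in Protocol 9.4.2.2, or define the comparator at 90 and 360 mg.
4. Say whether covariates are selected again on the normalised data.
5. Name Screening weight as the weight used.

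The cost is a SAP update to the derivation, model wording and labels. The protocol wording change needs IRB/IEC review and can wait for the next amendment. No new data are required.

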5.4.3.4 Analyses required for Other Objective (on Other PK endpoints)

The other PK parameters of UCB0599 and metabolites will be summarized by group and dose level using descriptive statistics as described in Section 5.3.1..

- For UCB0599: t_{max} , CL/F, Vz/F , $t_{1/2}$, $C_{max}/BW/D$, $AUC_{0-t}/BW/D$, and $AUC_{inf}/BW/D$. For t_{max} , only the median, IQR, minimum, and maximum will be reported.
- For **CCI** metabolites:
 - Metabolite/parent C_{max} and AUC ratio (corrected for the molecular weight of the entities), as appropriate
 - Metabolite/parent C_{max} and AUC ratio (corrected for the molecular weight of the entities) per group, as appropriate

5.5 Safety Analyses

Unless stated otherwise, all safety analyses will be performed on the SS.

5.5.1 Extent of Exposure

Administration of treatments will be listed by study part and sequence. Exposure data will be listed only.

5.5.2 Adverse Events

An Adverse Event is any untoward medical occurrence in a participant or clinical study participant, temporally associated with the use of study medication, whether considered related to the study medication.

Adverse events with start date/time prior to first treatment are defined as pre-treatment. These events will not be included in any tabulated summaries, but will be listed.

Treatment emergent AEs (TEAE) are all AEs starting on or after the date/time of first treatment and up to including 4 days after last treatment, or any unresolved event already present before administration of treatment that worsens in intensity following exposure to the treatment.

AEs with a start date after 4 days of last treatment are defined as post-treatment. These events will not be included in any tabulated summaries, but will be listed.

In case of missing or partially missing AE dates, the following rules will apply. Start and stop dates of AEs will be displayed as reported in the participant data listings (ie, no imputed values will be displayed in data listings).

The following rules will be applied for partial start dates and time:

- If only the month and year are specified and the month and year of the first treatment is not the same as the month and year of the start date, then use the 1st of the month, or the date of Screening if this is later (if the imputation results in an end date that is earlier than the start date, then use the 1st of the month). If time is missing, it will be imputed as 00:00 h
- If only the month and year are specified and the month and year of the first treatment is the same as the month and year of the start date, then use the date of the first treatment. If the imputed start date that is after the specified end date, then use the 1st of the month, or the date of Screening if this is later (if the imputation results in an end date that is earlier than the start date, then use the 1st of the month). If the imputed date is the date of treatment then time will be imputed as the start time of the treatment (ie, event will be regarded as treatment emergent)
- If only the year is specified, and the year of the first treatment is not the same as the year of the start date, then January 01 will be used. If time is missing, it will be imputed as 00:00 h
- If only the year is specified, and the year of the first treatment is the same as the year of the start date, then the date of the first treatment will be used. If this results in an imputed start date that is after the specified end date, then January 01, or the date of Screening if this is later will be used (if the imputation results in an end date that is earlier than the start date, then January 01 will be used). If the imputed date is the date of first treatment then time will be imputed as the start time of the treatment (ie, event will be regarded as treatment emergent)
- If the start date is completely unknown, then use the date of first treatment. If this results in an imputed start date that is after the specified end date, then use January 01 of the year of the end date, or the date of Screening if this is later.

The following rules will be applied for partial stop dates:

- If only the month and year are specified, then use the last day of the month
- If only the year is specified, then use December 31 of the known year
- If the stop date is completely unknown, do not impute the stop date

Missing or partially missing date and/or times will be imputed as described in [Table 5-7](#) for the calculation of duration of each AE. AE duration is computed and reported in day and time format.

Table 5-7: Calculation Rules for Duration of AEs

Data Availability	Onset Date/Time	Outcome Date/Time	Calculation Rules
Complete data	D1/T1	D2/T2	Duration = $(D2-D1)*24+(T2-T1)$
End time missing	D1/T1	D2/--	End time is substituted by time 23:59h (=23.98 in decimal format). Duration= $(D2-D1)*24+(23.98-T1)$
Start time missing	D1/--	D2/T2	Onset time is substituted by 00:00h. Duration= $(D2-D1)*24+T2$
Start and end time missing	D1/--	D2/--	Duration= $[(D2-D1)+1]*24$
Start day and time missing	--/--	D2/T2	Duration= $(D2-D0)*24+(T2-T0)$ For a participant in the SS, D0 and T0 are the date and time of the first administration of study medication and for screen failures, D0 is the date of the Screening Visit date and T0=00:00h.
End day and time missing	D1/T1	--/--	If the stop date is missing, duration will not be calculated.
Start and end date missing	--/--	--/--	If the stop date is missing, duration will not be calculated.

The duration of each AE will be calculated as follows and will be presented in dd:hh:mm format where dd represent days, hh: hours, and mm: minutes:

$$\text{Duration of AE} = \text{End date/time of AE} - \text{Start date/time of AE} \quad (5)$$

Adverse events will be assigned to Treatment Periods, based on the onset date/time of the AE. Assignment to Treatment Periods will be done after missing dates have been imputed as described above. AE will be assigned to a treatment based on the treatment received in the Treatment Periods as given in [Table 5-8](#).

Table 5-8: AE Treatment Period Assignment

Study Part	Period	Start	End
Part A	Treatment Period 1	Start date is on or after administration of treatment in Treatment Period 1	Prior to administration of treatment in Treatment Period 2
	Treatment Period 2	Start date is on or after administration of treatment in Treatment Period 2	Prior to administration of treatment in Treatment Period 3
	Treatment Period 3	Start date is on or after administration of treatment in Treatment Period 3	Prior to administration of treatment in Treatment Period 4
	Treatment Period 4	Start date is on or after administration of treatment in Treatment Period 4	Prior to administration of treatment in Treatment Period 5
	Treatment Period 5	Start date is on or after administration of treatment in Treatment Period 5	Prior to administration of treatment in Treatment Period 6
	Treatment Period 6	Start date is on or after administration of treatment in Treatment Period 6	
Part B	Treatment Period 1	Start date is on or after administration of treatment in Treatment Period 1	Prior to administration of treatment in Treatment Period 2
	Treatment Period 2	Start date is on or after administration of treatment in Treatment Period 2	

The following summaries will be provided for Part A by formulation and for Part B by dose level and group:

- Incidence of TEAEs – Overview
- Incidence of TEAEs
- Incidence of Serious AEs
- Incidence of TEAEs leading to discontinuation
- Incidence of TEAEs by maximum intensity
- Incidence of TEAEs by relationship to study medication

AEs will be presented as “number of participant (percentage of participant) [number of events]”. In this style of output, “[number of events]” will include all cases of an AE including repeat occurrences in individual participant, while “number of participant” will count each participant only once.

AEs will be presented by system organ class (SOC), high level term (HLT) and preferred term (PT) in a frequency table, giving the number of events, the number of participants, and the percentage of participants who experienced the event. Participants with multiple AEs are only counted once within each PT, each HLT and within each SOC.

Summaries by maximum severity will count each participant at most once within each MedDRA level based on the maximum severity/event intensity within that MedDRA level.

In summaries including intensity, the following intensity categories will be summarized: 'Mild', 'Moderate', 'Severe'. Participants who experience the same event multiple times will be included in the most severe category for tabulations by maximum intensity. Events with missing intensity will be considered as 'Severe' events for summary purposes but recorded as missing in the listings.

All summaries will be sorted alphabetically by SOC. Within SOC, it will be sorted by decreasing frequency of PT.

A by-participant listing will be presented for Part A by formulation and for Part B by dose level and group for all AEs for the SS. This will include reported term, SOC, PT, the onset date/time and outcome date/time of the event (including relative days), stop date and time (or ongoing, if applicable; relative days), the AE duration, severity, relationship, action taken, and outcome. In addition, the listing will flag TEAEs, SAEs, and AE of special interest. A glossary of AE terms including reported term, SOC and PT will also be presented.

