### **8.3.1        Time period and frequency for collecting AE and SAE information**

All AEs and SAEs will be collected from the signing of the ICF until the SFU Visit at the time points specified in the Schedule of Activities (Section 1.3 for Part A [[Table 1-3](#)] and Part B [[Table 1-4](#)]).

In order to ensure complete safety data collection, all AEs occurring during the study (ie, after the signing of the ICF), including any pretreatment and posttreatment periods required by the protocol, must be reported in the eCRF even if no study medication was taken but specific study procedures were conducted. This includes all AEs not present prior to the initial visit and all AEs that recurred or worsened after the initial visit.

All SAEs will be recorded and reported to the sponsor or designee within 24 hours, as indicated in Appendix 3 (Section 10.3). The Investigator will submit any updated SAE data to the Sponsor within 24 hours of it being available.

The Investigator is specifically requested to collect and report to UCB (or its representative) any SAEs (even if the Investigator is certain that they are in no way associated with the study medication), up to 30 days from the end of the study for each participant, and to also inform participants of the need to inform the Investigator of any SAE within this period. Serious AEs that the Investigator thinks may be associated with the study medication must be reported to UCB regardless of the time between the event and the end of the study.

The method of recording, evaluating, and assessing causality of AE and SAE and the procedures for completing and transmitting SAE reports are provided in Appendix 3 (Section 10.3).

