1.2.2 Part B

Part B of this study is an ethnobridging study evaluating the safety, tolerability, and PK of a single oral dose of the new UCB0599 formulation selected in Part A at 3 dose levels (90mg, 180mg, and 360mg) under normal gastric pH condition in healthy participants of Japanese and Chinese origins. Each group of ethnic origin (N=15 total for each) will be randomized to a 4-treatment, 6-sequence, 2-period crossover study using UCB0599:placebo in a 4:1 ratio, as shown below and in the Overall study schematic ([Figure 1-1](#)). Sequences 3 and 4 (Cohort 3) will only commence after Sequences 1 and 2 (Cohort 2) have been completed for all 5 participants; Sequences 5 and 6 (Cohort 4) will only commence after Sequences 3 and 4 have been completed for all 5 participants allowing the SMC review to be carried out before the start of Sequence 5 and 6.

- Sequence 1: placebo 90mg, followed by placebo 180mg (N=1)
- Sequence 2: UCB0599 90mg followed by UCB0599 180mg (N=4)
- Sequence 3: placebo 180mg, followed by placebo 360mg (N=1)
- Sequence 4: UCB0599 180mg, followed by UCB0599 360mg (N=4)
- Sequence 5: placebo 360mg, followed by placebo 90mg (N=1)
- Sequence 6: UCB0599 360mg, followed by UCB0599 90mg (N=4)

No participant will ever receive both UCB0599 and placebo, and therefore no intra-participant comparison will be possible; the crossover aspect of the Part B design refers to the dose level over 2 periods in order to limit the number of participants to be recruited into this study. This design will allow the collection of UCB0599 data at each dose level for 8 study participants of

each ethnic origin and the collection of dose-matching placebo data for 2 study participants of each ethnic origin for each dose. Participants will be blinded to the treatment (ie, UCB0599 or placebo), but not to the dosage within a sequence.

Part B consists of the following periods (for a total duration of up to 45 days):

- A 28-day Screening Period (2 to 28 days before administration of study medication)
- 2 treatment periods (for a total duration of up to 10 days)

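### SAP 5.5.2 counts a pre-dose event that worsens after dosing as a TEAE but also excludes it from all tables, and its onset-only assignment rule has no place for the worsening

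*SAP*

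**What the plan says.** SAP 5.5.2 first sets out the pre-treatment category: "Adverse events with start date/time prior to first treatment are defined as pre-treatment". Of that category it says: "These events will not be included in any tabulated summaries, but will be listed". No exception is made for events that later worsen.

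The TEAE definition follows. Besides events that begin after first treatment, it includes "any unresolved event already present before administration of treatment that worsens in intensity following exposure to the treatment".

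For attribution, the text above Table 5-8 says: "Adverse events will be assigned to Treatment Periods, based on the onset date/time of the AE". The earliest window in that table opens with this condition: "Start date is on or after administration of treatment in Treatment Period 1". The date of worsening is not used anywhere. The display is then fixed: "The following summaries will be provided for Part A by formulation and for Part B by dose level and group".

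On collection, Protocol 8.3.1 brings worsened events into reporting: "This includes all AEs not present prior to the initial visit and all AEs that recurred or worsened after the initial visit". It does not say which onset date a worsened event carries.

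**The concern.** Two rules in one section classify the same event in opposite ways, and neither is given precedence. Two programmers could each follow the SAP and produce different TEAE tables. If the TEAE definition is taken to prevail, Table 5-8 still offers no column for an event whose onset precedes the first dose.

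A related weakness arises between periods. The worsening clause refers to administration of treatment, not to first treatment, so it reads naturally onto each dose of a crossover. Onset-only assignment nevertheless leaves a Period 1 event with Period 1 even if it worsens after the Period 2 dose.

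Incidence of TEAEs is a primary safety endpoint in Part B and a secondary endpoint in Part A. Part B tabulates it by dose level and participant group in cells of 8 active participants, so a single case is visible.

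**Working it through.** **Inputs.** The Part B active sequences are in SAP 1.2.2, with 4 participants per origin in each: Sequence 2 (90mg then 180mg), Sequence 4 (180mg then 360mg) and Sequence 6 (360mg then 90mg). The Part A sequences are in SAP Table 1-3. The AE rules are in SAP 5.5.2 and Table 5-8.

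**Step 1: reproduce the plan's figure of 8 active participants per dose and origin.**
- 90mg: Sequence 2 + Sequence 6 = 4 + 4 = 8
- 180mg: Sequence 2 + Sequence 4 = 4 + 4 = 8
- 360mg: Sequence 4 + Sequence 6 = 4 + 4 = 8

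The figure reproduces.

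**Step 2: an event with onset before first treatment.** Take a mild headache that starts on Day -1 and becomes severe after the Day 1 dose.

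| Rule in SAP 5.5.2 | Result |
|---|---|
| TEAE definition, worsening clause | TEAE |
| Pre-treatment definition | Pre-treatment, listed only |
| Table 5-8, onset rule | No period, so no dose or formulation |

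The tables show 0 or 1 TEAE depending on which sentence is followed. If 1, no column is available for it.

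**Step 3: an event that crosses periods.** Take a Sequence 4 participant with mild nausea from Day 4 (after 180mg), unresolved, and severe after 360mg on Day 6. Assume one AE record that carries its highest intensity.

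| Table and dose | As written | Worsening assigned to its own period |
|---|---|---|
| Any TEAE, 180mg | 1/8 | 1/8 |
| Any TEAE, 360mg | 0/8 | 1/8 |
| Severe TEAE, 180mg | 1/8 | 0/8 (mild kept) |
| Severe TEAE, 360mg | 0/8 | 1/8 |

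**Step 4: size of one case.** 1/8 = 12.5 points per origin; 1/16 = 6.25 points with origins pooled.
- TEAE incidence: 180mg is unchanged and 360mg changes by 12.5 points, provided the participant has no other TEAE in that row at 360mg.
- Severe TEAEs, 360mg minus 180mg: -12.5 as written and +12.5 after reassignment, a change of 25 points.

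**Step 5: direction of the between-period effect.** In Sequences 2 and 4 the earlier dose is the lower one: 4 + 4 = 8 of 12 active participants per origin, 16 of 24 overall (66.7%). In Sequence 6 it is the higher one: 4 of 12 per origin, 8 of 24 overall (33.3%).

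**Step 6: how many cases.** The documents give no rate. As an assumption, let each active participant have probability w of a Period 1 event that worsens after the Period 2 dose.

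| w | Expected of 24 (24w) | Placed at the lower dose (16w) | Placed at the higher dose (8w) |
|---|---|---|---|
| 5% | 1.2 | 0.8 | 0.4 |
| 10% | 2.4 | 1.6 | 0.8 |
| 25% | 6.0 | 4.0 | 2.0 |

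**Step 7: Part A.** Every UCB0599 dose is 180mg, so the effect is on formulation. In all six sequences the formulation changes at each of the five transitions between periods, including Period 3 to Period 4. A worsening at any of them is shown under the previous formulation.

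**The case against.** The strongest reply is that everything beyond the clash of wording depends on how a worsening is recorded. If the site opens a new AE entry with its own start date, both effects disappear. Protocol 8.2.1 says that worsening of earlier examination findings is recorded as an AE, and Appendix 3 (10.3) counts an exacerbation of a pre-existing condition as meeting the AE definition. Both lean towards a new entry. The follow-up part of the same appendix sends updated information to the original eCRF, which leans the other way. None of these fixes an onset date, and the eCRF Completion Guidelines are not among the documents. SAP 6.1.5 (data derivation rules) is marked not applicable. The dependency therefore stands as a limit on the point, not as an answer to it.

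A second reply is that attribution by onset is a coherent choice for events that begin after the Period 1 dose: they are TEAEs and they are tabulated. That is right. The between-period part is a weakness of attribution, not a contradiction. It matters because the SAP's own worsening clause has nowhere to take effect.

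A third reply is that nothing is hidden, because every AE is listed with dates, severity and a TEAE flag. This is true of the listings. The flag, however, rests on the same unresolved definition.

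A reader might also infer that the rule takes TEAEs from the higher dose, adds them to the lower one, and so flattens or reverses the dose-safety pattern. The documents do not support that. In the Sequence 4 example the nausea did begin after 180mg, so its count there is correct and only 360mg loses a case. A third of active participants are affected in the opposite direction. No frequency is given, and Protocol 2.3 describes most earlier TEAEs as mild or moderate and resolved.

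**Conclusion.** The contradiction in SAP 5.5.2 is real for events with onset before first treatment. They are both TEAEs and excluded from the tables, and Table 5-8 gives them no column. It would be too strong to say that such events will be dropped: the text leaves the outcome undetermined.

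The between-period effect holds in a smaller form. A Period 1 event that worsens after the Period 2 dose shows its worsened intensity under the Period 1 treatment and nothing under the Period 2 treatment. One case changes TEAE incidence at the later dose by up to 12.5 points per origin, or 6.25 points pooled. The 25-point figure belongs only to the severe contrast in the maximum-intensity table and should not be read as a shift in the primary safety endpoint.

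These sizes assume that a worsening stays in the original record and, for the maximum-intensity table, that the record carries its highest intensity. The number of cases is unknown and probably small. The point is worth settling because the cells hold 8 participants and the correction is cheap.

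**What to change.** Three changes before database lock:

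1. In SAP 5.5.2, limit the pre-treatment sentence. Suggested text: *AEs with onset before first treatment that do not worsen in intensity after treatment are classed as pre-treatment.*
2. Add to the text above Table 5-8: *An AE that worsens in intensity after an administration is counted as a TEAE of the period in which it worsened, at the worsened intensity, using the date/time of worsening. The intensity before worsening stays with the original period, or with pre-treatment.*
3. Have the eCRF completion guidelines capture the date and time of worsening, for example as a new AE entry.

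The cost is two SAP sentences and one data-entry instruction. The downside is that one continuing episode may appear in two dose or formulation columns, which a table footnote should explain.
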